8 TRIAL DESIGN

8.1 Endpoints

8.1.1 Primary Assessment

IMP tolerability and safety during the first 4 weeks of treatment.

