14.2.3.2 Adverse Events

AEs will be coded using the MedDRA. Events will be identified as treatment-emergent (TEAE) and non-treatment-emergent (Non-TEAE) on the basis of the date of onset relative to the date of the first IMP dose.

Separate analyses will be presented for all TEAEs, for potentially IMP related TEAEs, for all serious TEAEs, and for serious, potentially treatment related TEAEs. TEAEs will be considered potentially IMP related if the investigator's rating of the causal relationship is anything other than 'not related' or missing.

Summaries (number and percentage of events as well as of patients with any events of a particular type) of TEAEs (by system organ class [SOC] and preferred term [PT]) will be provided. Number (%) of patients experiencing TEAEs by severity, relationship to IMP, seriousness, and action taken with regard to IMP will be summarized. Number (%) of patients with TEAEs leading to discontinuation of clinical trial participation will also be summarized.

Treatment group comparisons of the proportion of patients with TEAEs will be based on Wilson score confidence intervals [[Wilson, 1927](#)]. Pairwise comparisons between all treatment groups will be provided at the SOC level as well as for the events identified as local tolerability measures in [Section 12.1.5](#). For the latter, separate analyses will be presented for all events with onset during the first 4 weeks of treatment and for events with onset at any time during randomized treatment.

Incidence densities of events per patient day starting with the first IMP administration will be determined for all TEAEs as well as separately for each of the events identified as local tolerability measures in Section 12.1.5. In accordance with the visit schedule, incidence densities will be provided for the periods between every two adjacent visits starting with the first IMP administration as well as for the entire randomized treatment period. Events will be assigned to their period of onset.

In addition to the pairwise treatment group comparisons, all analyses specified above in this section will also be performed for the comparison between all patients treated with L-CsA (2 x 5 mg/day or 2 x 10 mg/day) and those treated with placebo in order to increase the chance of identifying TEAEs potentially related to L-CsA.

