## **9.2 Sample Size Considerations**

This is a Phase IIa study in a rare indication, with very limited availability of eligible patients and a purely descriptive statistical concept. Accordingly, the sample size for the study was established based on considerations of feasibility rather than on power calculations.

A total of 24 patients (3 arms with 8 patients in each) are planned to be randomized.

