## 13 PRIMARY ASSESSMENTS

The primary assessments will be measures of safety and local tolerability listed in Section 8.3 and covering the first 4 weeks of treatment, defined as data collected until Visit 3. AEs will be included into this analysis if their date of onset lies on or before Visit 3 or, in case of an incomplete or missing date of onset, if they could have started on or before Visit 3 in accordance with all available information, using the procedure for incomplete data information already described in Section 12 above.

Outcomes assessed during study visits will be included into the primary analysis up until Visit 3 scheduled to be performed at Week 4 after baseline, or until the EoT visit if it was performed on or before Visit 3.

All analyses described in this chapter will be performed on the SAF.

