### 13.1 Analysis of Local Tolerability

In accordance with the study protocol, local tolerability events of interest (i.e., cough, wheezing, bronchospasm, throat irritation, and change in FEV1) will be documented in the eCRF as AEs. During data analysis local tolerability events of interest thus have to be identified from the CRF form of AEs as follows:

- MedDRA (version 23.1) Preferred Terms (PTs):
  - Cough (MedDRA code 10011224)
  - Wheezing (MedDRA code 10047924)
  - Bronchospasm (MedDRA codes 10006482, 10072338)
  - Throat irritation (MedDRA code 10043521)
  - Change in FEV1 (MedDRA codes 10016987, 10016989, 10016985)
- The version of the utilized dictionary will be presented either in the title or footnote of the provided tables and listings.
- The event must have newly appeared within 1 hour after the end of an IMP inhalation.
- They must have occurred within on or before Visit 3.
- Events meeting the criteria above will be selected independently of the causality assessment of the investigator.

For each local tolerability event, pairwise treatment group comparisons of the proportion of patients with at least one local tolerability event will be performed based on Wilson score 95% confidence intervals (Wilson, 1927).

---

Moreover, incidence densities of events per patient treatment day starting with the first IMP administration will be determined separately for each local tolerability event. In accordance with the visit schedule, incidence densities will be provided for the periods between every two adjacent visits starting with the first IMP administration for the entire randomized treatment period up until Visit 3, and for entire randomized treatment period (as secondary assessment, please refer to section 8.4). Events will be assigned to their period of onset.

In addition to the pairwise treatment group comparisons, all analyses specified above in this section will also be performed for the comparison between all patients treated with L-CsA (2 x 5 mg/day or 2 x 10 mg/day) and those treated with placebo.

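### SAP 13.1 compares the five local tolerability events one by one and states no comparison of patients with any of them; with 8 per arm, a reaction spread over several terms can easily be missed

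*SAP*

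**What the plan says.** Protocol 8.1.1 gives the primary assessment as "IMP tolerability and safety during the first 4 weeks of treatment". SAP 13 repeats this: "The primary assessments will be measures of safety and local tolerability listed in Section 8.3".

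SAP 13.1 takes five local events (cough, wheezing, bronchospasm, throat irritation, change in FEV1) from the adverse event form by MedDRA code. It adds a timing condition: "The event must have newly appeared within 1 hour after the end of an IMP inhalation". The comparison is then set out as: "For each local tolerability event, pairwise treatment group comparisons of the proportion of patients with at least one local tolerability event will be performed", using 95% Wilson score intervals. Rates follow the same pattern: "incidence densities of events per patient treatment day starting with the first IMP administration will be determined separately for each local tolerability event". All of this is repeated for pooled L-CsA against placebo, and SAP 14.1 extends it to the whole treatment period.

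Protocol 14.2.3.2 plans pairwise comparisons for the local events without saying whether each is taken alone. For incidence densities it is explicit: "separately for each of the events identified as local tolerability measures".

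On size, SAP 9.2 states: "A total of 24 patients (3 arms with 8 patients in each) are planned to be randomized". The number rests on feasibility, and no event rate or detectable difference is given.

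**The concern.** The five terms are different names for what may be one airway response to an inhaled product. If the same irritant reaction is recorded under different terms in different patients, a term-by-term layout divides one effect over several sparse rows. Five terms by four contrasts (three pairwise, one pooled) make 5 × 4 = 20 intervals, with no line saying how many patients had any local reaction.

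That proportion is the most direct answer to the trial's main question. SAP 13.3.1 gives such a line for adverse events in general (patients with any treatment-emergent event) but none is stated for local tolerability. SAP 13.3.1 also pools the doses expressly to raise the chance of finding drug-related events. Counting each patient once over the five terms serves the same aim.

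**Working it through.** **Inputs from the documents.** 3 arms × 8 = 24 patients, so 8 v 8 pairwise and 16 v 8 pooled; five terms; two-sided 95% Wilson intervals (SAP 9.1, 9.2, 13.1). There is no power figure to reproduce.

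**Assumptions.** The documents give no event rates, no pattern of spread over terms, and no method for turning two Wilson intervals into a comparison. I use the Newcombe interval, which is built from Wilson limits, and check non-overlap of the two Wilson intervals as a variant. An effect counts as shown when the interval for the difference excludes zero.

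**Step 1: what one row needs.** For x of n, p = x/n and z = 1.96:

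- Wilson limits = [p + z²/2n ± z√(p(1−p)/n + z²/4n²)] / (1 + z²/n)
- Newcombe lower limit = (p1 − p2) − √[(p1 − l1)² + (u2 − p2)²], where l1 is the lower Wilson limit on active and u2 the upper one on placebo

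For 0/8, u2 = 0.324. For 3/8, l1 = 0.137; for 4/8, l1 = 0.215.

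- 3/8 v 0/8: 0.375 − √(0.238² + 0.324²) gives −2.7 points (interval −2.7 to 69.4), which includes zero.
- 4/8 v 0/8: 0.500 − √(0.285² + 0.324²) gives +6.8 points (6.8 to 78.5), which excludes zero.

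With one placebo event, a row needs 5/8 v 1/8. Pooled, it needs 7/16 v 0/8.

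**Step 2: one worked trial.** Suppose 6/8 v 1/8 have any local event: difference 62.5 points, interval 13.9 to 83.1. Let the six patients fall over the five terms as 2, 1, 1, 1, 1. No row then excludes zero:

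- 2/8 v 0/8: −12.0 to 59.1
- 1/8 v 0/8: −21.5 to 47.1
- 2/8 v 1/8: −26.4 to 48.1

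**Step 3: how often.** Assume 60% v 10% with any local event, 8 v 8, over the four symptom terms. On active, 0.60 × 8 = 4.8 patients react; at one term each that is 4.8 / 4 = 1.2 per row, against a threshold of 4. The any-event chance is an exact binomial sum; the single-term chances are simulated, with further terms always different from the first.

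| Spread over terms | At least one single term | Any local event |
|---|---|---|
| 1 term per patient | 7% | 63% |
| 1.5 terms | 23% | 63% |
| 2 terms | 44% | 63% |
| 3 terms | 68% | 63% |
| 1 term, 80% coded as cough | 43% | 63% |

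Pooling the doses does not cure it: at 1 term per patient, 16 v 8, the chances are 2% and 73%. At 3 terms they are 74% and 73%.

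With five equal terms at 62.5% v 12.5%, 8 v 8, the any-event row gives 63%, against 5%, 16%, 32% and 58% for 1, 1.5, 2 and 3 terms.

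**Step 4: the interval method.** By non-overlap of the two Wilson intervals, a row needs 6/8 v 0/8 or 7/8 v 1/8. At 60% v 10%, 8 v 8, the any-event row then shows the effect in 18% of trials, not 63%.

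**Step 5: the system organ class row as a substitute.** SAP 13.3.1 plans Wilson comparisons at this level, without the 1-hour window. Assume 75% v 12.5% with a local event, all five terms in one class, and a background rate b of other events there. The class rates are 1 − 0.25(1 − b) and 1 − 0.875(1 − b). At b = 0, 20% and 40% these are 75% v 12.5%, 80% v 30% and 85% v 47.5%. The chance of showing the difference is 84%, 63% and 40%.

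**The case against.** The case against has five parts.

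- **Other analyses aggregate.** The class-level comparisons count a patient once per class, and SAP 13.2 compares the CGI side-effects dimension and the Investigator's Tolerability Assessment between arms. A reader might infer that tolerability as a whole is judged only term by term. The documents do not support that. The cover is still partial. The class rows drop the 1-hour window, and the class of each term is not stated. The ratings come from investigators who know the treatment (Protocol 8.3.1). Visit 3 may be remote, where CGI cannot be assessed and the schedule marks no tolerability rating.
- **The sentence is ambiguous.** Its closing words could describe a composite. This stands. 'For each' favours the per-term reading, and if a composite was meant the text still needs rewording.
- **The yardstick is not the plan's.** The trial is purely descriptive, with no working hypothesis. A reader might infer that twenty intervals including zero would be taken as good tolerability. No rule in either document says so, and counts and by-patient listings are planned.
- **Patients may report several terms.** Protocol 12.1.5 has the listed events actively solicited before inhalation at each visit except the last, so multiple terms per patient are plausible. This stands: a spread effect can still show, and at about 3 terms nothing is lost.
- **The method is unnamed.** This stands too. A reader might infer that the combined row would reliably reveal a large effect. By non-overlap it would not.

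**Conclusion.** The point holds as a missing pre-specified summary. As SAP 13.1 most naturally reads, a primary assessment has no patient-level line for any local reaction, and a reaction spread over terms can easily be missed with 8 per arm. At an assumed 60% v 10%, the any-event row shows the difference in 63% of trials, against 7% to 44% for at least one single term when affected patients report 1 to 2 terms each. The loss shrinks to 63% v 43% if 80% of reactions are coded as cough, and vanishes at about 3 terms per patient.

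All these figures rest on assumed rates, an assumed spread and the Newcombe interval. The finding concerns the layout of the local-event analysis. It is not a criticism of the sample size, which the plan sets by feasibility and does not claim to power.

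**What to change.** In SAP 13.1, and through 14.1 for the 12 weeks:

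- Add 'any local tolerability event' (at least one of the five terms, same 1-hour window) as the leading row of the pairwise and pooled comparisons, each patient counted once for the proportion. Give the same row for the incidence densities, and state whether two terms arising from one inhalation count as one event or two.
- Keep the five single-term rows beneath it.
- Reword the comparison sentence so that the per-term and any-term proportions are named separately.
- Name the interval method for the difference between two proportions.

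The cost is one row per table from data already collected. The combined row mixes terms of different clinical weight, which the five rows beneath it make visible. Fixing it before database lock avoids a choice made after the results are seen.

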	
3. Chronic renal dysfunction with serum creatinine ≥ 2.5 mg/dL.4. Chronic hepatic dysfunction with serum total bilirubin > 5x upper limit of normal (ULN), transaminases > 5x ULN, or alkaline phosphatase > 5x ULN.5. Evidence of clinical relapse of the primary malignancy, according to investigator's judgement, which warranted allogeneic bone marrow transplant.6. Use of azithromycin within 4 weeks prior to Randomization (Visit 1).7. Chronic oxygen use or use of non-invasive ventilation.8. Active smokers (i.e. any kind of inhaled nicotine consumption).9. Pregnant women or women who are unwilling to use appropriate birth control to avoid pregnancy over the course of the clinical trial (for details see Appendix II).10. Women who are currently breastfeeding.11. Known hypersensitivity to L-CsA or to cyclosporine A.12. Patients with life-expectancy of less than 6 months.13. Receipt of an investigational drug as part of a clinical trial within 4 weeks prior to the Screening Visit. Participation in registries, is allowed.14. Psychiatric disorders or altered mental status precluding understanding of the informed consent process and/or completion of the necessary procedures.15. Any co-existing medical condition that in the Investigator's judgment will substantially increase the risk associated with the patient's participation in the clinical trial.16. Pre-scheduled hospitalizations, surgeries or interventions planned to be performed after obtaining Informed Consent for this study.
Investigational Medical Product:	The L-CsA/Liposomal Placebo is supplied in glass vials containing 10 mg or 5 mg of L-CsA or 0 mg L-CsA. The 10 mg L-CsA or placebo lyophilisate is reconstituted with 2.4 mL 0.25% NaCl and the 5mg L-CsA lyophilisate is reconstituted with 1.2 ml 0.25% NaCl to obtain a ready to use dispersion for inhalation via the L-CsA CCI .
Mode of Administration/ Dosing Schedule:	The investigational medicinal product (IMP) will be administered bid by inhalation (morning/evening). At every visit, one dose administered via inhalation will be monitored by the clinical trial center personnel. Nebulization time per inhalation dose is approximately 5-10 minutes for the 5 mg dose and 8-13 minutes for the 0 and 10 mg doses.

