6.1.1 Drug Component

L-CsA consists of the active substance CsA and excipients as described in the Investigator's Brochure (IB). L-CsA is a lyophilisate for reconstitution with 0.25% saline. The formulation is developed for inhalation use and is therefore adjusted to a physiological tolerable value of pH 6.5 ± 0.3 and an osmolality of 430-550 mOsmol/kg in the reconstituted formulation.

The liposome size in the reconstituted formulation is in the range of 40-100 nm with a polydispersity index (PI) of not more than 0.50, which indicates the width of the size distribution. PI values above 0.5 indicate a broad distribution.

The doses of 0 mg and 10 mg L-CsA are reconstituted in a total volume of 2.5 mL. The 5 mg L-CsA dose is reconstituted in a total volume of 1.25 ml. The entire volume of the reconstituted solution is used per aerosol administration.

Additional information can be found in the IB.

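### Placebo is volume-matched only to the 10 mg arm, so the pooled and 5 mg vs placebo contrasts for local tolerability should be labelled as unmatched and not used to attribute events to L-CsA

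*SAP*

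**What the plan says.** **Volumes and times.** Protocol 6.1.1 states: "The doses of 0 mg and 10 mg L-CsA are reconstituted in a total volume of 2.5 mL". It continues: "The 5 mg L-CsA dose is reconstituted in a total volume of 1.25 ml". It adds: "The entire volume of the reconstituted solution is used per aerosol administration". The protocol synopsis gives nebulization times of "approximately 5-10 minutes for the 5 mg dose and 8-13 minutes for the 0 and 10 mg doses". No 1.25 mL placebo is described.

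**Analysis.** For each local event (cough, wheezing, bronchospasm, throat irritation, change in FEV1), SAP 13.1 plans comparisons with Wilson intervals: "pairwise treatment group comparisons of the proportion of patients with at least one local tolerability event will be performed based on Wilson score 95% confidence". It then adds the pooled contrast: "all analyses specified above in this section will also be performed for the comparison between all patients treated with L-CsA" (5 mg and 10 mg combined) and those on placebo. Events count if they newly appear within 1 hour after an inhalation ends, whatever the investigator's causality rating. SAP 14.1 repeats the analyses for the whole treatment period. SAP 13.3.1 applies the same pooling to the SOC-level adverse event comparisons.

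**Purpose of pooling.** Protocol 14.2.3.2, which covers the local tolerability events, says the pooling is done "in order to increase the chance of identifying TEAEs potentially related to L-CsA".

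Neither document mentions the volume difference in connection with these contrasts. SAP 13.7 lists no sensitivity analysis.

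**The concern.** A placebo comparison attributes events to the drug only if the arms otherwise receive the same thing. For local events just after inhalation, the amount of vehicle and the time spent inhaling could matter in themselves. On both, placebo matches 10 mg and does not match 5 mg.

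If inhaling the vehicle provokes some cough or throat irritation, the 5 mg arm starts from a lower background than placebo. Pooling carries half of that deficit into the combined L-CsA group. A contrast added to make drug-related events easier to find could then make local ones harder to find.

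The SAP's event definition adds weight to this. The 1-hour window selects inhalation-triggered events, and causality ratings are set aside, so attribution rests on comparing arms. The pooled row also has the most patients (16 vs 8) and is likely to be cited.

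**Working it through.** **Inputs from the documents.** 24 patients randomized 1:1:1, 3 × 8 = 24 (Protocol 14.5). Volumes and times as quoted above. No event rates are stated, so every risk below is an assumption.

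**Step 1: size of the mismatch.**
- Concentration: 10/2.5 = 5/1.25 = 4 mg/mL, so halving the dose halves the volume.
- 5 mg vs placebo volume: 1.25/2.5 = 50%.
- Pooled mean volume: (2.5 + 1.25)/2 = 1.875 mL, which is 75% of 2.5 mL.
- Midpoint nebulization time: 7.5 vs 10.5 minutes, or 71%.

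**Step 2: bias if risk is linear in volume.** Let v be the vehicle-driven risk at 2.5 mL, and assume v/2 at 1.25 mL. With no drug effect:
- 5 mg vs placebo: v/2 − v = −v/2
- pooled vs placebo: (v + v/2)/2 − v = −v/4
- 10 mg vs placebo: 0

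| Placebo vehicle risk v | 5 mg vs placebo (points) | Pooled vs placebo (points) |
|---|---|---|
| 0% | 0 | 0 |
| 10% | −5 | −2.5 |
| 20% | −10 | −5 |
| 40% | −20 | −10 |

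**Step 3: check with a different curve and a drug effect.** Take risk = 1 − exp(−(a × volume/2.5 + d × dose/10)), where a is the vehicle hazard and d the drug hazard. Choose d so that 10 mg exceeds placebo by 10 points. The last column gives the 5 mg arm the full 2.5 mL, purely to separate dose dilution from volume.

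| Placebo risk | Pooled, no drug effect | Pooled, 10 mg excess +10 | Same, if 5 mg were volume-matched |
|---|---|---|---|
| 0% | 0 | +8 | +8 |
| 20% | −5 | +3 | +8 |
| 40% | −9 | 0 | +8 |
| 50% | −10 | −2 | +8 |

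The fall from +10 to +8 is dilution by the lower dose. The further fall is due to volume, and it disappears at a placebo risk of 0%.

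**Step 4: what 8 per arm can show.** Suppose counts of placebo 4/8, 10 mg 6/8 and 5 mg 3/8, with Wilson limits combined into an interval for the difference:
- 10 mg vs placebo: +25 points (95% CI −19 to +59)
- 5 mg vs placebo: −13 points (−50 to +30)
- pooled, 9/16 vs 4/8: +6 points (−30 to +41)

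**Step 5: does leading with 8 vs 8 lose sensitivity?** Use the Step 3 model with placebo 20% and 10 mg 50%. The chance that the 95% interval lies wholly above zero is 28% for 10 mg vs placebo and 13% for the pooled contrast. With a volume-matched 5 mg arm the pooled figure would be 18%. The 10 mg contrast was also ahead of the pooled contrast at the planned volumes in the seven other assumed settings tried (placebo 10% to 50%, excess 30 or 40 points).

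**The case against.** **The matched contrast is already there.** The pairwise set includes 10 mg vs placebo and the pooled comparison is an addition, so a reader can see the components beside it. Both documents describe the statistical concept as purely descriptive, and no decision rule acts on the pooled result. This stands, and it limits the point to labelling and interpretation.

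**The mechanism is not shown.** Neither document says that the liposomal vehicle causes local events or that they rise with volume. Protocol 6.1.1 describes pH and osmolality as adjusted to tolerable values. The vehicle-related intolerance in Protocol 5.1.1 belongs to the earlier propylene glycol formulation. That makes vehicle effects a fair question for an inhaled cyclosporine but does not establish them here. A reader might infer that the pooled and 5 mg contrasts are biased. The documents support only that they can be, and at zero vehicle risk the volume bias is zero.

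**The size is below the trial's resolution.** One patient in an arm of 8 is 12.5 points, more than the largest pooled bias tabulated. This is true of formal inference. It does not protect against a near-zero or negative point estimate being read as reassurance.

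**Each dose is tested as delivered.** A smaller volume is part of the 5 mg regimen, and the objective is tolerability of each regimen against placebo. That is a fair use of 5 mg vs placebo. It does not license reading the difference as an effect of L-CsA itself.

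**Should the pooled local analysis be dropped?** A reader might conclude so. Protocol 14.2.3.2 specifies it as a safety output. Removing it would create a protocol-SAP difference to record in SAP section 6, and the same event terms would remain in the pooled SOC tables.

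**Conclusion.** The point holds as one of interpretation. The facts are exact: the 5 mg arm inhales half the placebo volume, the pooled group averages 25% less than placebo, and the SAP attaches no caveat. Whether this biases the results depends on whether local events vary with vehicle volume or inhalation time, and the documents leave that open. If risk is linear in volume, the pooled bias is one quarter of the placebo vehicle risk and the 5 mg vs placebo bias is one half, both favouring L-CsA. An exponential curve gives similar figures.

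The documents do not support saying that a drug effect will be masked, or that the primary assessment is invalid, because the matched 10 mg vs placebo contrast is retained. The 10 mg vs 5 mg contrast changes dose and volume together. That is part of the design and should be stated as a limitation; no SAP wording can separate the two. Overall this is a cheap improvement worth making.

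**What to change.** In SAP 13.1, and in 14.1 for the 12-week analysis:

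1. Keep all planned comparisons.
2. Name 10 mg vs placebo as the contrast for attributing local tolerability events to L-CsA.
3. Label the pooled and 5 mg vs placebo results as not volume-matched, and state that a null or negative difference there is not evidence of no drug effect. Put the same label on local-event terms in the pooled SOC-level tables of SAP 13.3.1.
4. State as a limitation that 10 mg vs 5 mg cannot separate dose from volume.

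This costs a few sentences and table footnotes; no planned output is lost and neither design nor data collection changes. The downside is that attribution rests on 8 vs 8 patients instead of 16 vs 8. In the settings of Step 5 that does not reduce the chance of detecting an excess, but those settings are assumed and the intervals will be wide in any case.
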